9.5 Aerobic Training /Resistance Training/ Progressive Stretching Discontinuation

Permanent treatment discontinuation is defined as cessation of aerobic training, resistance training or progressive stretching administration. When appropriate, follow up assessments will still be performed.

Temporary treatment interruption due to an adverse event is not considered permanent discontinuation. Patients whose treatment is interrupted due to an adverse event and then restarted will continue to have regularly scheduled study visits. In both experimental groups, the intensity and duration of the next scheduled session will be reviewed and discussed by ExOnc exercise personnel. However, if a participant misses more than 6 weeks of continuous sessions, the participant will begin the intervention from the starting prescription, due to the anticipated impact of deconditioning during the 6 weeks of intervention interruption.

9.6 Concomitant Medications

All concomitant medications at the time of study entry will be identified through a medical chart review and recorded in REDCap. Participation in the study intervention must not impact use of concomitant medications at any stage of the study period.

9.7 Effects of Aerobic Training or Resistance Training on Exposure to Other Conventional/ Novel Anticancer Therapies

There is no clinical data on the effect of aerobic training and/or resistance training (or progressive stretching) on the therapeutic index of anticancer agents used in the management of lung cancer.. All clinical studies to date have focused on the effects of exercise training interventions to prevent and/or mitigate the psychosocial and/or physiological side-effects of cancer therapy; whether exercise training influences the pharmacodynamics (PD) or pharmacokinetics (PK) of anticancer therapy has not been investigated.

9.8 Effects of Conventional/Novel Anticancer Therapies on Aerobic Training or Resistance Training

Our group, as well as others, have demonstrated that different forms of anticancer therapy causes unique and varying degrees of damage to various components of the cardiopulmonary system (heart-lung-blood-muscle axis). Collectively, these effects lead to significant and marked declines in global cardiopulmonary function, manifest as poor exercise tolerance (decreased V_{O2peak}). A major rationale for this trial is to determine the optimal exercise training modality to mitigate and/or reverse this phenotype in patients with lung cancer.

10.0 EVALUATION DURING TREATMENT/INTERVENTION

All evaluations being conducted during the treatment intervention, including the window of time in which conduct of these tests is required, are described in the schedule of activities (Table 1). Further details are provided herein. Assessments which are initially completed at baseline, midpoint and follow up may be repeated at the investigators discretion.

10.1 CPET

At the end of week 8, participants in the aerobic training arm (Arm A) and the combined aerobic and resistance training arm (Arm C) will repeat the cardiopulmonary exercise test. This test is repeated at this period to re-assess V_{O2peak} under the expectation that V_{O2peak} is likely to have improved in the first 8 weeks of the program. Thus, information from the second test is used to re-prescribe exercise training prescription to ensure continual cardiovascular adaptations across the entire study period. This test will not be repeated in the resistance training group (Arm B) or the progressive stretching group (Arm D).

10.2 1-RM Testing

At the end of Week 8, participants in the resistance training arm (Arm B) and the combined aerobic and resistance training arm (Arm C) will repeat the one repetition maximum strength test. This test is repeated at this period to re-assess lower and upper body strength under the expectation that these parameters would have improved in the first 8 weeks of the program. Thus, information from the second test is used to re-prescribe exercise training prescription to ensure continual strength adaptations across the entire study period. This test will not be repeated in the aerobic training group (Arm A) or the progressive stretching group (Arm D).

10.2 Fasting Blood Draws

At baseline and study follow-up, participants will undergo a fasting blood draw to obtain peripheral blood for complete blood count (CBC), and secondary endpoints. The CBC will be resulted by MSK clinical labs. In addition, data will be collected on any CBC tests that are performed as part of standard of care while the patient is on study.

Research blood samples will be collected, processed and stored per the Lab Manual.

11.0 TOXICITIES/SIDE EFFECTS

Toxicity grading will be performed in accordance with NCI CTCAE, v 4.03. Adverse clinical symptoms that occur during or immediately following intervention sessions -with the exception of the expected heart rate, blood pressure, and SpO₂ changes that are related to exercise - will be reported as adverse events. Adverse events will be reviewed by the exercise physiologist, and graded and attributed accordingly at the end of each session. Adverse events that are not resolved at the end of a session will be reviewed with the patient during the next scheduled session to assess whether or not the event is still ongoing. During the intervention phase, adverse events requiring adjustments to the two study aerobic training prescription approaches will be made according to the ExOnc Exercise Physiology standards of care and/or at the discretion of the Program Director.

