6.0 CRITERIA FOR SUBJECT ELIGIBILITY

6.1 Subject Inclusion Criteria

- Signed informed consent prior to initiation of study-related procedures
- Age 21-80
- Weight <205 kgs
- ECOG 1
- Diagnosed with histologically confirmed lung cancer, regardless of disease stage and receiving any prior line of any therapy in the context of metastatic disease
- An interval of at least three months following the completion of primary resection, if appropriate
- An interval of no longer than ten years following completion of primary therapy, if appropriate
- Life expectancy 4 months
- Performing less than 150 minutes of structured moderate-intensity or strenuous-intensity exercise per week.
- Exercise intolerance (i.e., patients must have a VO₂peak below that predicted for active age and sex-matched individuals)
- Willing to be randomized to one of the study arms
- Willing to commit to the study program and comply with all related protocol procedures
- Able to achieve an acceptable peak baseline CPET, as defined by any of the following criteria:
 - achieving a plateau in oxygen consumption, concurrent with an increase in power output;
 - a respiratory exchange ratio 1.10;
 - attainment of maximal predicted heart rate (HRmax) (i.e., within 10 bpm of age-predicted HRmax [HRmax = 220-Age[years]]);

- volitional exhaustion, as measured by a rating of perceived exertion (RPE) 18 on the BORG scale.
- Able to complete an acceptable baseline CPET in the absence of high risk ECG findings or other inappropriate response to exercise as determined by the PI.
- Ability to achieve and complete an acceptable baseline one-repetition maximum muscular strength test as defined by the effective execution of protocol-specific joint and muscle ranges of motion without remarkable signs or symptoms of pain, discomfort or distress.

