7.2 Screening Identification Numbers

Study site personnel will maintain a screening log for all potential study participants, and will assign a screening identification (ID) number in consecutive order as listed on the screening log. The screening ID number will be used on all study forms and laboratory specimens throughout the study.

A new screening ID number will be assigned to a patient who is rescreened after originally failing to meet study eligibility.

For patients who provide informed consent and subsequently do not meet eligibility criteria, or withdraw consent, study site personnel will ensure that the source record includes appropriate documentation, such as eligibility criteria reviewed, protocol procedures performed, and reason for screen failure.

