9.3 Intervention Attendance and Adherence

Attendance is calculated as the number of intervention sessions attended divided by the total number of planned sessions (i.e., 3 times/wk x 16 weeks= 48). *Adherence* is defined as the number of scheduled training sessions attended, as well as whether the training session dose was

successfully completed (i.e., participant completed the intervention session at the planned duration and intensity) divided by the total number of planned sessions (i.e., 48).

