- o *Physical Functioning* will be assessed using the physical functioning subscale (PF) of the Short-Form (SF) 36.⁵¹ The physical functioning subscale is a 6-item self-report questionnaire. The PF uses a mixture of item types. Item 1 queries about overall health, scored on a 5-point scale ranging from excellent to poor. Item 2 queries about limitations to normal activities of daily living including participation in vigorous and moderate activities. All items are rated on a 3-point Likert scale from yes, limited a lot to no, not limited at all. Item 3 queries about limitations relating to work over the past 4 weeks using a dichotomized response (yes vs. no). Item 4 queries about bodily pain over the past 4 weeks ranging from none to extremely. Item 5 queries about pain during the normal work week ranging from not at all to extremely. Finally, item 6 asks 4 statements asking about general health perceptions scored on 5-point Likert scale ranging from definitely true to definitely false. The sum of item 2 yields a measure of physical functioning ranging from 0 to 20. Other items will be considered and summed as single items. Higher scores indicate higher physical functioning. The SF-36 has well established internal consistency and test-retest reliability.⁵¹
- *Safety* will be evaluated by the type and prevalence of adverse events during study-related assessments as well as exercise training sessions. The type and nature of SAEs considered in this trial include those DLTs listed in Section 9.3 as well as those events listed in Section 11.1 (the unanticipated but possible adverse events associated with CPET, 1RM, aerobic training or resistance training).

Tracking and monitoring of exercise-related adverse events will be assessed using the following methods:

1. Stringent monitoring and recording (in the patient REDCAP) of physiologic outcomes and vital signs (e.g., heart rate, blood pressure, etc.) prior to, during, and following every intervention session.
2. At the beginning of each week, the exercise specialist will spend the first 10 minutes of every session discussing any potential negative side-effects of the intervention assignment and any injuries that may have occurred. All events will be recorded in the patient REDCAP.
3. Early stopping rules in response to a differential higher frequency of adverse events in a particular study group as identified in planned interim analyses (see **Section 14.0**).

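### Safety is defined to include events at study assessments, but the general reporting rule covers only intervention sessions, and the stopping rules and DLT list that 12.2 relies on are not in the sections it names.

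*Combined protocol and SAP*

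**What the plan says.** Section 12.2 sets the scope of the endpoint: safety "will be evaluated by the type and prevalence of adverse events during study-related assessments as well as exercise training sessions". It then gives three tracking methods. The first is physiologic monitoring around every intervention session. The second is a weekly enquiry at training, "discussing any potential negative side-effects of the intervention assignment and any injuries that may have occurred". The third is "Early stopping rules in response to a differential higher frequency of adverse events in a particular study group as identified in planned interim analyses", with a pointer to Section 14.0. For serious events, 12.2 says that those considered "include those DLTs listed in Section 9.3 as well as those events listed in Section 11.1".

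Section 11.0 gives the general reporting rule. It covers "Adverse clinical symptoms that occur during or immediately following intervention sessions", and the exercise physiologist reviews and grades events when each session ends.

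Other provisions bear on the point:
- Section 12.1 defines CPET-related events and has them recorded in REDCap.
- Section 6.1 requires a baseline 1RM test completed "without remarkable signs or symptoms of pain, discomfort or distress".
- For consented patients found ineligible, Section 7.2 asks for source documentation "such as eligibility criteria reviewed, protocol procedures performed, and reason for screen failure".
- Section 17.2 requires serious adverse event reporting from consent until 30 days after the last intervention.
- Section 17.0 says that the safety analysis takes in all patients.

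**The concern.** The endpoint is wider than the rule that feeds it. A non-serious event at a 1RM test, six-minute walk, chair stand or other functional test falls within the safety definition, but no stated rule requires it to be reported and graded at the time. If it goes unrecorded, the assessment part of the safety result could be too low. Week 17 tests come after randomization, so a difference between arms there could also be missed. Baseline tests precede allocation and affect only the overall event rate for the tests.

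The cross-references matter for a different reason. A reader of 12.2, including an ethics reviewer, would believe that a between-arm stopping rule and a defined list of dose-limiting events protect patients. The plan specifies neither.

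**Working it through.** The plan states no figure to reproduce here. The check traces each assessment to the stated capture routes, follows each pointer to its target, and then counts tests.

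**1. Capture routes by time point, non-serious events, assessments other than CPET**

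| Time point | Route in the text | Left open |
|---|---|---|
| Baseline, later randomized | Weekly enquiry once training starts | Mainly short-lived symptoms |
| Baseline, screen failure | Source record of the reason (7.2) | No graded event; no later session |
| Week 8 (1RM in Arms B and C, per 10.2) | Weekly enquiry | Mainly short-lived symptoms |
| Week 17 | None stated if training has ended | Reporting and grading |

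Training lasts 16 weeks, so a Week 17 test normally has no later session at which to ask. At baseline, remarkable pain or distress on the 1RM makes the patient ineligible under 6.1. Patients with such an event are therefore the ones directed to the screen-failure record.

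**2. The pointers**

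- 12.2 to 9.3: Section 9.3 begins "Attendance is calculated as the number of intervention sessions attended divided by the total number of planned sessions" and goes on to adherence. It lists no DLTs, and no such list appears elsewhere in the text.
- 12.2 to 14.0: Section 14 holds the sample size (14.1) and the endpoint analyses (14.2). It has no interim look, threshold or boundary.
- 12.2 to 11.1: Section 12.2 says this list covers 1RM and resistance training. The expected effects in 11.1 are headed by CPET, two aerobic doses and stretching.

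**3. How many 1RM assessments are exposed**

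The MSK allocation is A 16, B 17, C 16, D 18, a total of 67 (Section 1.0).
- Scheduled 1RM assessments in randomized MSK patients: 67 baseline + 33 at Week 8 (17 + 16) + 67 at Week 17 = 167. Week 17 is 67/167 = 40%.
- Allowing for drop-out: 70 of 78 operable first-site patients completed (16.02), so 67 × 70/78 = 60. If 80% are retained (an assumption, since MSK also enrols advanced disease), 67 × 0.80 = 54.
- Baseline tests that end in screen failure come on top; their number is not given.

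The documents give no event rate for these tests. At assumed rates of 1%, 3% and 5%, 60 tests yield 0.6, 1.8 and 3.0 events, and the chance of at least one, 1 − (1 − r)^60, is 45%, 84% and 95%. These are chances that an event occurs. They are not chances that it goes unrecorded, which the documents do not allow one to estimate.

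**4. Would writing a stopping rule into 14.0 be better than deleting the claim?**

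As an illustration, take a look after 8 MSK patients per arm, which leaves 8 + 9 + 8 + 10 = 35 of the 67 places open. Pause an exercise arm if its patients with an event exceed Arm D's by c or more. With independent binomial counts, detection is P(X_arm − X_D ≥ c). A false pause of any arm is 1 − Σ_j P(X_D = j) ∏ P(X_arm ≤ j + c − 1). All rates and thresholds are assumptions.

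| Rule | False pause, all 5% / all 10% | Detects 20% vs 5% / 30% vs 5% |
|---|---|---|
| MSK only, c = 3 | 1.2% / 5.3% | 15% / 35% |
| MSK only, c = 2 | 11% / 24% | 39% / 63% |
| Both sites pooled (A 32, B 31, C 32, D 30), c = 6 | 0.4% / 3.5% | 37% / 79% (Arm B) |

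The pooled figures assume that the harm was already present in the 23 first-site Arm B patients. If those patients had a 5% rate and the harm arises only in the 8 MSK patients, pooled detection falls to 1.6% or 4.6%. Pooling dilutes the signal in the only patients whom a pause could still protect.

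**The case against.** The strongest reply is that the plan already intends to count these events and has other protection. Section 12.2 puts assessments in scope, and 17.0 promises individual tabulation of adverse events. The schedule allows Week 17 visits a window of two weeks either way and lets them be split, so some tests may precede the last session. Appendix H, the exercise physiology guidelines, and the unit's standards of care were not supplied and may already require recording at tests. Serious events are covered from consent. The monitoring committee has unblinded data (7.4), 16.2 describes institutional committees, 17.0 names an independent board, 9.4 allows session-level modification, and the study is classed as minimal risk.

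Much of this stands. It limits the gap to non-serious events and leaves its size unknown. It does not close the gap: an intention to analyse is not a collection step, and 11.0 does not send the reader to Appendix H for events at tests. Section 13.0 mentions safety follow-up only after discontinuation and does not describe it.

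A reader might go further and infer that the safety result will be under-counted, that the 45% to 95% figures measure lost events, or that patients have no between-arm protection. The documents support none of these. Recording may happen in practice, the percentages describe occurrence at assumed rates, and committee review exists without a stated boundary.

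**Conclusion.** The point holds as an internal inconsistency in the safety plan that merits correction. Non-serious events at assessments other than CPET have no general reporting and grading rule, and they could be missed at Week 17 and in baseline screen failures. The exposure is up to 67 Week 17 1RM assessments at MSK (60 or 54 under the retention assumptions above), plus functional tests and an uncounted number of failed baselines. The loss itself cannot be estimated. It would be zero if Appendix H or local practice already captures these events.

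The two empty pointers in 12.2, to DLTs in 9.3 and to interim analyses in 14.0, are certain on the supplied text. Both target sections are present and deal with other matters.

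It might seem to follow that a formal stopping rule must be supplied. The illustrative calculations do not support that. An early MSK-only look either detects little or pauses falsely too often, and a pooled rule does worse when the harm is new at MSK. The primary VO2peak analysis is not affected.

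**What to change.** 1. In 11.0, extend "Adverse clinical symptoms that occur during or immediately following intervention sessions" by adding *and study assessments*, with grading at the end of each session or test, from consent through Week 17. If Appendix H already covers this, cite it there.
2. Tabulate assessment events over all tests started in consented patients, including screen failures, by time point, and by arm after randomization.
3. Delete the stopping-rule claim in 12.2. State instead that the monitoring committee reviews adverse events by arm without a formal boundary. Do not add a rule that pools first-site patients.
4. Replace the pointer to DLTs in 9.3 with an actual event list that includes musculoskeletal injury and events from resistance training and 1RM testing.

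The cost is a short event record per assessment, a small by-arm table from the statistician, who already has unblinded access, and one amendment. No visits, tests or patients are added. Section 16.01 exempts amendments that affect MSK only from review at the other site, and this one may qualify because the first site is closed to enrolment. If not, the first site's IRB has 90 days to approve it.

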11.1 Side Effects

Anticipated (expected) side-effects associated with a symptom-limited CPET, the two aerobic training doses, or progressive stretching include:

- Fatigue
- Myalgia
- Arthralgia
- Back pain
- Shortness of breath (dyspnea)

Unanticipated but possible side-effects that are *rare, but serious* include:

- Cardiovascular: angina, hypotension, palpitations, rebound hypertension, syncope
- Arrhythmias
- Heart attack
- Stroke

12.0 CRITERIA FOR THERAPEUTIC RESPONSE/OUTCOME ASSESSMENT

12.1 Primary Study End Point

Exercise Capacity (VO_{2peak}): VO_{2peak} will be evaluated using a magnetically braked cycle ergometer test with 12-lead ECG monitoring (Mac® 5000, GE Healthcare) performed by trained exercise physiologists.

Cardiopulmonary exercise testing is considered the gold standard assessment of exercise capacity and provides assessment of peak oxygen consumption (VO_{2peak})- Expired gases will be analyzed continuously by a metabolic measurement system (Parvo Medics TrueOne 2400). After stable resting metabolic values have been achieved (including blood pressure and heart rate), participants will begin cycling at a participant-specific designated power output for 1 minute and the power output

will be increased every minute until exhaustion or a symptom-limited peak is achieved measured by peak oxygen consumption ($VO_{2\text{peak}}$) ($\text{mL}\cdot\text{kg}^{-1}\text{min}^{-1}$).

Acceptable test criteria for this assessment include any of the following: (1) a plateau or decrease in oxygen consumption concurrent with increased workload, 2) heartrate 220-age (± 10 beats) (3) a respiratory exchange ratio =1.1, (4) volitional exhaustion, a rating of perceived exertion 18. This protocol has been previously demonstrated to be appropriate for measuring $VO_{2\text{peak}}$ in our prior studies of early-stage and advanced cancer patients. ^{36,37}

All participants will be monitored continuously with 12-lead ECG during exercise and five minutes of recovery. During exercise, oxyhemoglobin saturation will be monitored continuously using finger pulse oximetry while blood pressure will be measured manually by auscultatory sphygmomanometer every two minutes.

Exercise testing-related events were operationalized as any event occurring during this procedure. SAEs will be defined as the occurrence of any of the following: (1) significant angina, (2) sustained ventricular tachycardia, (3) myocardial infarction, (4) external defibrillation or implantable cardioverter-defibrillator discharge, (5) syncope, (6) provision of cardiac life support medications, (7) direct admission to emergency room, or (8) death. A positive test was defined as identification of any of the following ECG changes: (1) significant ischemic changes in ECG during exercise or recovery or (2) development of exercise induced bundle branch block. Criteria for ischemic changes in ECG included 0.1 mV deviation of the ST segment horizontal to or away from the baseline isoelectric line at 0.08 seconds after the J-point in the absence of significant resting ST-T abnormalities or left bundle branch block. ST segment changes toward the isoelectric line will not be considered positive, regardless of the magnitude of change. If the baseline ECG reveals a J-ST segment depression >0.05 mV, a "double criteria" (an additional 0.2 mV) of ST depression will be required with the appropriate horizontal or downsloping morphology to qualify as a positive test.

Clinical exercise physiologists within the ExOnc at MSK will perform all cardiopulmonary exercise tests. All personnel are trained to read (but not interpret) exercise ECG's and are trained in Advanced Cardiovascular Life Support (ACLS). All tests will only be conducted when physician coverage on the clinical floor is available.

All cardiopulmonary exercise testing will be conducted in Cardiology Service space either at Main Campus or in the Outpatient Facility on 53rd Street, or at the Sidney Kimmel Center for Prostate and Urologic Cancers, on designated ExOnc equipment specifically designated for research purposes.

If any ECG abnormalities are observed either prior to, during, or after the exercise test, all procedures will be immediately stopped. At this point, a cardiologist will be asked to review the ECG to determine the appropriate course of action. The participant will not be allowed to leave the facility until such an examination has been performed by the physician. All events will be recorded in the participants REDCAP. The participants attending oncologist will be informed of this event (by email) within 12 hours of the event.

Due to the presence of significant, and potentially clinically important, variability in CPET procedures (VO_{2peak} measurement), all potential participants will perform a second CPET at baseline to account for potential learning effects and variability.³⁰ If both the first and second CPET achieve acceptable test criteria, results of the second test will be used in all protocol procedures and statistical analyses.

